5.2 Analysis Sets

Three analysis sets will be used: the Full Analysis Set (FAS), the Per-Protocol Analysis set (PPAS), and the SafAS.

5.2.1 Full Analysis Set

There will be 3 FASs for this study. Immunogenicity analyses will be performed on the FAS for exploratory purposes.

5.2.1.1 Full analysis set 1 (FAS1) for infant vaccination (< 12 months of age):

The FAS1 is defined as the subset of all randomized subjects who received at least 1 dose of the study vaccine^a in infancy (at Visit 1 to Visit 3, < 12 months of age) and have a valid post-vaccination serology result in infancy. All subjects will be analyzed according to the treatment group to which they were randomized.

5.2.1.2 Full analysis set 2 (FAS2) for immunogenicity persistence evaluation:

The FAS2 is defined as the subset of all randomized subjects who received at least 1 dose of the study vaccine in infancy (at Visit 1 to Visit 3, < 12 months of age) and have a valid pre-vaccination serology result at Visit 5 before the 12-month vaccination for Subgroups 1a and 2a or at Visit 6 before the 15-month vaccination for Subgroups 1b and 2b. All subjects will be analyzed according to the treatment group to which they were randomized.

5.2.1.3 Full analysis set 3 (FAS3) for 2nd year of life vaccination (≥ 12 months of age):

The FAS3 is defined as the subset of all randomized subjects who received at least 1 dose of the study vaccine in the 2nd year of life (≥ 12 months of age) and have a valid post-vaccination serology result in the 2nd year of life. All subjects will be analyzed according to the treatment group to which they were randomized.

5.2.2 Per-Protocol Analysis Set

Immunogenicity analyses will primarily be performed on PPAS. The PPAS is a subset of the FAS. There will be 3 per-protocol analysis sets (PPAS) corresponding to the 3 FASs:

- PPAS for infant vaccination (PPAS1)
- PPAS for immunogenicity persistence evaluation (PPAS2)
- PPAS for 2nd year of life vaccination (PPAS3)

^a A study vaccine is any vaccine that is administered as part of the study, including the investigational product (MenACYW conjugate vaccine), the control vaccine (Mencevo®) and the study-specific routine vaccines.

5.2.2.1 Per-Protocol Analysis Set 1 (PPAS1)

Serology obtained 30 days after the last vaccination visit at 6 months of age for all antigens will be used for immunogenicity analyses of infant stage of the study.

The subjects presenting with at least one of the following relevant protocol deviations during infancy will be excluded from the PPAS1:

- Subject did not meet all protocol-specified inclusion criteria or met at least one of the protocol-specified exclusion criteria
- Subject did not complete the vaccination schedule for infant year of the study
- Subject received a vaccine other than the one that he / she was randomized to receive
- Preparation and / or administration of vaccine was not done as per-protocol
- Subject did not receive vaccine in the proper time window:
 - Visit 1: 42 to 89 days of age
 - Visit 2: Visit 1 + 60 days (+14 days)
 - Visit 3: Visit 2 + 60 days (+14 days)
- Subject did not provide a post-dose serology sample in the proper time window or a post-dose serology sample was not drawn:
 - Blood sampling 2: Visit 3 + 30 days (+21 days)
- Subject received a protocol-prohibited therapy, medication or vaccine.
- Subject had other protocol violations that affected the subject's immune response, as determined by the clinical team before locking the database.

In addition to the reasons listed above, subjects will also be excluded from the PPAS1 if their serology sample did not produce a valid test result.

Vaccine correctness required by the PPAS1 includes not only the 3 doses of MenACYW conjugate vaccine or MENVEO®, but also the concomitant vaccines as scheduled (Pentacel®, PCV13, rotavirus, and hepatitis B) during infant stage.

In the event of a local or national immunization program with a pandemic influenza vaccine or coronavirus vaccine or any other vaccine as needed, subjects who receive one or more doses of the pandemic influenza or corona virus vaccine at any time during the study will not be withdrawn from the study.

5.2.2.2 Per-Protocol Analysis Set 2 (PPAS2)

Pre-vaccination serology obtained at Visit 5 before 12-month vaccinations for Subgroups 1a and 2a or Visit 6 before 15-month vaccinations for Subgroups 1b and 2b will be used for immunogenicity persistence analyses.

The subjects presenting with at least one of the following relevant protocol deviations during infancy will be excluded from the PPAS2:

- Subject did not meet all protocol-specified inclusion criteria or met at least one of the protocol-specified exclusion criteria
- Subject did not complete the vaccination schedule for infant year of the study
- Subject received a vaccine other than the one that he/she was randomized to receive
- Preparation and/or administration of vaccine was not done as per-protocol
- Subject did not receive vaccine in the proper time window:

- Visit 1: 42 to 89 days of age
- Visit 2: Visit 1 + 60 days (+14 days)
- Visit 3: Visit 2 + 60 days (+14 days)
- A pre-dose serology sample at Visit 5 for Subgroups 1a or 2a before 12-month vaccinations or Visit 6 for Subgroups 1b and 2b before 15-month vaccinations was not drawn.
- Subject received a protocol-prohibited therapy, medication or vaccine.
- Subject had other protocol violations that affected the subject's immune response, as determined by the clinical team before locking the database.

In addition to the reasons listed above, subjects will also be excluded from the PPAS2 if their serology sample did not produce a valid test result.

Vaccine correctness required by the PPAS2 includes not only the 3 doses of MenACYW conjugate vaccine or MENVEO®, but also the concomitant vaccines as scheduled (Pentacel®, PCV13, rotavirus, and hepatitis B) during infant stage.

In the event of a local or national immunization program with a pandemic influenza vaccine or coronavirus vaccine or any other vaccine as needed, subjects who receive one or more doses of the pandemic influenza or corona virus vaccine at any time during the study will not be withdrawn from the study.

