2.2 Secondary Objectives

- 1) To demonstrate the non-inferiority of immune responses of the routine pediatric vaccines administered concomitantly with MenACYW conjugate vaccine as compared with MENVEO® in infants and toddlers 6 weeks old to 18 months old.
- 2) To assess the antibody responses against meningococcal serogroups A, C, Y, and W after the administration of the 4th dose of MenACYW conjugate vaccine or MENVEO® when both are given concomitantly with routine pediatric vaccines at 12 months of age.
- 3) To assess the persistence of bactericidal antibodies at 12 months of age in subjects who previously received 3 doses of MenACYW conjugate vaccine or MENVEO® in infancy concomitantly with routine pediatric vaccines at 2, 4, and 6 months of age.
- 4) To describe the antibody responses against the antigens of the routine pediatric vaccines (Pentacel®, Prevnar 13®, M-M-R® II, VARIVAX®, RotaTeq®, and ENGERIX-B®) when administered concomitantly with either MenACYW conjugate vaccine or MENVEO®
- 5) To describe the antibody responses against meningococcal serogroups A, C, Y, and W when MenACYW conjugate vaccine versus (vs) MENVEO® is administered concomitantly with routine pediatric vaccines.
- 6) To describe the antibody responses against meningococcal serogroups A, C, Y, and W when MenACYW conjugate vaccine is administered to children 12 to 15 months of age vs when MenACYW conjugate vaccine is administered to children 15 to 18 months of age, concomitantly with routine pediatric vaccines (Subgroup 1a vs Subgroup 1b), including the bactericidal antibodies persistence and the effect of 4th dose of MenACYW conjugate vaccine at 12 to 15 months of age or 15 to 18 months of age.

^ahSBA vaccine seroresponse for serogroups A, C, Y, and W is defined as:

- For a subject with a pre-vaccination titer < 1:8, the post-vaccination titer must be $\geq 1:16$
- For a subject with a pre-vaccination titer $\geq 1:8$, the post-vaccination titer must be ≥ 4 -fold greater than the pre-vaccination titer

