3.2 Study Plan

Vaccination

A schedule of assessments and study vaccinations is provided in the Tables of Study Procedures and in [Table 3.1](#).

Blood Sampling

All subjects in the study will have 4 blood draws each. [Table 3.1](#) presents the schedule for blood-sampling. The schedule of antigen testing is detailed in [Table 3.2](#).

^a Subjects in Subgroup 1a will complete the last study visit at 13 to 16 months of age. For subjects in Subgroup 1a, the 4th dose of Pentacel® which is administered at 15 to 18 months of age, will be provided by the Sponsor for completion of the DTaP series with vaccine from the same manufacturer, as per ACIP recommendation. The study personnel / Investigator will be responsible for administering this dose at the recommended age outside of the scope of the study.

^b First dose of HB vaccine must be given at least 28 days prior to study enrollment.

Table 3.1: Vaccination and blood sampling schedule

Age in months	2 months		4 months		6 months		7 months		12 months		13 months		15 months		16 months	
	Visit #	Visit 1		Visit 2		Visit 3		Visit 4		Visit 5*		Visit 6: 1a† and 2a		Visit 7: 1b and 2b Visit 8: 2a		
Group		Blood Draw‡	Vaccines	Vaccines	Vaccines	Blood Draw	Subgroup	Blood Draw‡	Vaccines	Blood Draw	Vaccines	Blood Draw‡	Vaccines	Blood Draw	Vaccines	Blood Draw
1	X	MenACYW Pentacel PCV13 rotavirus hepatitis B§	MenACYW Pentacel PCV13 rotavirus	MenACYW Pentacel PCV13 rotavirus	MenACYW Pentacel PCV13 rotavirus hepatitis B	X	1a	X	MenACYW MMR varicella PCV13	X	MMR varicella PCV13	No study visit	X	MenACYW Pentacel hepatitis A	X	
2	X	MENVEO Pentacel PCV13 rotavirus hepatitis B§	MENVEO Pentacel PCV13 rotavirus	MENVEO Pentacel PCV13 rotavirus	MENVEO Pentacel PCV13 rotavirus hepatitis B	X	2a	X	MENVEO MMR varicella PCV13	X	MMR varicella PCV13	No study visit	X	Pentacel hepatitis A	X	

*Visit 5 will occur at 12 months of age for Subgroups 2a and 2b, and at 12 to 15 months of age for Subgroups 1a and 1b.

†Last study visit for Subgroup 1a. Routine vaccine can be administered as per standard of care after study procedures are completed. Visit 6 will occur at 13 to 16 months of age for Subgroup 1a. For Subgroup 2a Visit 6 occurs at 13 months of age.

‡Blood will be drawn prior to vaccinations.

§ The first dose of HB vaccine must have been received at least 28 days prior to the first study vaccination at Visit 1.

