Trial termination record (termination of active portion of the trial)											X	

IRT: interactive response technology

*This call is made 8 days after the respective vaccinations. If day 8 falls on a weekend or holiday, the telephone call may be made on the following business day. During this telephone call, the staff will find out whether the subject experienced any SAE (including AES) and/or MAAE not yet reported and will remind the subject's parent/guardian to continue using the diary card, to bring the diary card to the study center at the next visit, and confirm the date and time of the next visit

†Staff will contact the subject's parent/ guardian by telephone within 14 days before V05 to remind them about the forthcoming study visit. If the subject's participation in the study is discontinued, the information recorded on the diary card will be reviewed at this time and the diary card will be retrieved by the site.

‡At V05, subjects must be between 12 and 15 months of age (from the day subjects become 12 months old until the day before becoming 16 months old).

§Staff will contact the subject's parent/ guardian by telephone at 6 months (+ 30 days) after the last vaccination visit to identify the occurrence of any SAEs (including any AESIs) and MAAEs not yet reported. The final telephone call will continue until contact is made or 28 days have passed at which time the subject will be considered lost to follow-up.

**Physical examination should be done as per standard of care.

††Temperature needs to be measured before each vaccination and recorded in the source documents.

†††Should a subject receive oral or injectable antibiotic therapy within 3 days prior to any blood draw, the investigator will postpone that blood draw until it has been 3 days since the subject last received oral or injectable antibiotic therapy. Postponement must still be within the timeframe for blood draw. If postponement would result in the sample collection falling outside of this timeframe, the blood sample should be collected without postponement, and it should be documented appropriately that the sample was taken less than 3 days after stopping antibiotic treatment.

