Immediate surveillance (30 min)	X		X		X					X		X		X		
Diary card (DC) provided	DC1		DC2		DC3		DC4		DC5		DC6		DC7			
Telephone call		X		X		X		X		X		X		X		

Visit / Contact	Visit 1	Telephone contact (TC)1*	Visit 2	TC2*	Visit 3	TC3*	Visit 4	TC4†	Visit 5‡	TC5*	Visit 6	Visit7§	TC6*	Visit 8	TC7**	Follow-up Contact
Diary card reviewed and collected			DC1		DC2		DC3		DC4		DC5	DC6		DC7		
Recording of solicited injection site and systemic AEs	X		X		X				X			X				
Recording of unsolicited AEs																
Collected from D0 to D30 after each vaccination																
Reporting of serious adverse events (SAEs, including AESIs) and medically-attended AEs (MAAEs)****																
To be reported throughout the study																
Collection of reportable concomitant medications	X		X		X		X		X		X	X	X	X	X	
Memory aid (MA) provided††††															MA	
Trial termination record (termination of active portion of the trial)														X		

IRT: interactive response technology

*This call is made 8 days after the respective vaccinations. If day 8 falls on a weekend or holiday, the telephone call may be made on the following business day. During this telephone call, the staff will find out whether the subject experienced any SAE (including AESI) and/or MAAE not yet reported and will remind the subject's parent/guardian to continue using the diary card to bring the diary card to the study center at the next visit, and confirm the date and time of the next visit.

†Staff will contact the subject's parent/ guardian by telephone within 14 days before V05 to remind them about the forthcoming study visit. If the subject's participation in the study is discontinued, the information recorded on the diary card will be reviewed at this time and the diary card will be retrieved by the site.

‡At V05, subjects must be 12 months of age (from the day subjects become 12 months old until the day before becoming 13 months old).

§At V07, Subjects must be between 15 and 18 months of age (from the day subjects become 15 months until the day before becoming 19 months of age).

**Staff will contact the subject's parent/ guardian by telephone at 6 months (+ 30 days) after the last vaccination visit to identify the occurrence of any SAEs (including any AESIs) and medically-attended AEs not yet reported. The final telephone call will continue until contact is made or 28 days have passed at which time the subject will be considered lost to follow-up.

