
hSBA meningococcal serogroups A, C, Y, and W antibody titers for Group 1 and Group 2:
 
 30 days after the 3rd dose (after the 6-month vaccination) 	
 RCDCs hSBA meningococcal serogroups A, C, Y, and W antibody titers $\geq 1:4$ and $\geq 1:8$ hSBA meningococcal serogroups A, C, Y, and W antibody titers \geq 4-fold rise from pre- vaccination (D0) to post-vaccination hSBA vaccine seroresponse

hSBA meningococcal serogroups A, C, Y, and W antibody titers:
 
 30 days after the 4th dose (after the 12-month vaccination) for Subgroup 1a and Subgroup 2a 30 days after the 4th dose (after the 15-month vaccination) for Subgroup 1b 	
 RCDCs hSBA meningococcal serogroups A, C, Y, and W antibody titers $\geq 1:4$ and $\geq 1:8$ hSBA meningococcal serogroups A, C, Y, and W antibody titers \geq 4-fold rise from pre-vaccination (D0) to post-dose 4 vaccination hSBA vaccine seroresponse

hSBA meningococcal serogroups A, C, Y, and W antibody titers to evaluate the immune persistence of MenACYW:
 
For Subgroup 1a and Subgroup 2a (persistence at 12 month), Subgroup 1a and Subgroup 1b (persistence at 12 month vs 15 month):
 
 30 days after the 3rd dose (after the 6-month vaccination) D0 before the 4th dose (before the 12-month vaccination for Subgroup 1a and before the 15-month vaccination for Subgroup 1b) 	
 hSBA meningococcal serogroups A, C, Y, and W antibody titers $\geq 1:4$ and $\geq 1:8$

Antigens, Time Points and Groups	Endpoints

hSBA meningococcal serogroups A, C, Y, and W antibody titers to evaluate the effect of 4th dose of MenACYW: For Subgroup 1a and Subgroup 1b (12 mo vs 15 mo):
 
 1. D0 before the 4th dose (before the 12-month vaccination for Subgroup 1a and before the 15-month vaccination for Subgroup 1b) 2. 30 days after the 4th dose (after the 12-month vaccination for Subgroup 1a and after the 15-month vaccination for Subgroup 1b) 	
 • hSBA meningococcal serogroups A, C, Y, and W antibody titers \geq 4-fold rise from pre-4th dose vaccination to post-4th vaccination

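### The 1a vs 2a comparison of hSBA persistence at 12 months allows later blood sampling in the MenACYW subgroup, and no planned analysis accounts for time since dose 3

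*SAP*

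**What the plan says.** SAP 2.2 gives Objective 3 as "To assess the persistence of bactericidal antibodies at 12 months of age in subjects who previously received 3 doses" of either vaccine. The persistence row of SAP Table 5.3 labels 1a vs 2a as persistence at 12 months, and 1a vs 1b as "persistence at 12 month vs 15 month".

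The persistence sample is drawn at Visit 5, before vaccination, in 1a and 2a. A footnote to SAP Table 3.1 states that "Visit 5 will occur at 12 months of age for Subgroups 2a and 2b, and at 12 to 15 months of age" in the MenACYW subgroups. The footnotes to the procedure tables give exact limits:
- Subgroup 1a (Table 3.4): "from the day subjects become 12 months old until the day before becoming 16 months old".
- Subgroup 2a (Table 3.6): "from the day subjects become 12 months old until the day before becoming 13 months old".

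PPAS2 (SAP 5.2.2.2, and protocol 12.2.3.2 in the same terms) lists time windows for Visits 1 to 3 only. For the persistence sample itself ("A pre-dose serology sample at Visit 5 for Subgroups 1a or 2a before 12-month vaccinations") the sole grounds for exclusion are that it was not drawn or gave no valid result. FAS2 (SAP 5.2.1.2) has no timing limit either. By contrast, PPAS1 excludes on timing ("Subject did not provide a post-dose serology sample in the proper time window or a post-dose serology sample was not drawn"), and PPAS3 applies both the Visit 5 and 6 age windows and a post-dose sampling window.

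The planned persistence summaries are titers and the percentages at or above 1:4 and 1:8. The additional analyses in SAP 5.1.5 cover blood-sample handling, race, gender, preterm birth and COVID-19. None uses age at sampling or time since dose 3.

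**The concern.** A persistence titer depends on how long antibody has had to wane. In the 1a vs 2a contrast, only the MenACYW subgroup can be sampled on schedule more than about 7.6 months after dose 3. Randomization does not balance this, because the difference is part of the visit schedule of each arm. If titers fall over that period, the table headed as 12-month persistence mixes a vaccine comparison with a difference in elapsed time, and the distortion runs against MenACYW. The quantity named in Objective 3, antibody at 12 months of age, is then not quite the quantity tabulated for 1a.

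**Working it through.** The documents give no figure for the persistence comparison, so there is none to reproduce. The check has two parts: window arithmetic from the documents, then an illustration under stated assumptions.

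**Inputs from the documents**
- Dose 3 at 164 to 224 days of age, both arms (protocol 5.1.4.1, Visit 3).
- Visit 5 from 12 months to the day before 16 months in 1a, and to the day before 13 months in 2a.

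**Interval from dose 3 to the persistence sample** (1 month = 365.25/12 = 30.44 days)
- Dose 3 age: 164/30.44 = 5.39 months to 224/30.44 = 7.36 months.
- 1a: 12 − 7.36 = 4.6 months to 16 − 5.39 = 10.6 months (about 141 to 322 days).
- 2a: 12 − 7.36 = 4.6 months to 13 − 5.39 = 7.6 months (about 141 to 231 days).
- Width of the Visit 5 window: about 121 days in 1a and 29 days in 2a.

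**Assumptions, none of them in the documents**
- Four patterns of visit timing within each window, applied alike to both arms.
- Log-linear waning at the same true rate in both arms, with a half-life h of 90 to 365 days.
- SD of 2 log2 units for titer, and 50% or 70% of 2a at or above 1:8.

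**Mean timing gap (1a minus 2a)**
- Uniform: half the difference in widths, about (121 − 29)/2 = 46 days.
- Skewed early (triangular, mode at 12 months): one third of the difference, about 30 days.
- Skewed late (triangular, mode at the end of the window): two thirds, about 61 days.
- Clustered at 12 months (exponential delay, mean 20 days, truncated at the window): about 8.5 days.

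**Effect of timing alone.** GMT ratio = 2^(−gap/h). For uniform visits, 2^(−45.7/90) = 0.70 and 2^(−45.7/365) = 0.92. The differences in the percentage at or above 1:8 come from simulation.

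| Visit pattern | Gap (days) | 1a/2a GMT ratio, h = 90 to 365 | Difference in % ≥ 1:8 (points) |
|---|---|---|---|
| Clustered at 12 months | 8.5 | 0.94 to 0.98 | −2 to −0.4 |
| Skewed early | 30 | 0.79 to 0.94 | −7 to −1.4 |
| Uniform | 46 | 0.70 to 0.92 | −10 to −2 |
| Skewed late | 61 | 0.63 to 0.89 | −13 to −3 |

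**Scale.** With 770 and 385 children (the evaluable numbers in SAP 5.6; the size of PPAS2 is not stated), the 95% CI half-width for a difference is 1.96 × √[p(1 − p)(1/770 + 1/385)]. That is 6.1 points at p = 50% and 5.6 points at p = 70%. With uniform visits and a short half-life, the timing effect would exceed sampling error. With clustered visits it would not.

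**Assay floor.** The GMT ratios above ignore the SAP rule that values below the LLOQ (1:4) are set to half the LLOQ. For a gap of 1.5 months, an SD of 2 log2 units and 60% at or above 1:8, applying the rule changes the ratio from 0.59, 0.77 and 0.84 to 0.63, 0.79 and 0.85 for half-lives of 2, 4 and 6 months. The GMT effect is therefore somewhat smaller than tabulated.

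**Share of 1a kept by a common limit of 12 months to the day before 13 months:** 29/121, about 24% (188 of 770), with uniform visits; 43% if skewed early, 77% if clustered and 6% if skewed late.

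**The case against.** The unequal windows are disclosed design. Primary Hypothesis 1 itself sets MenACYW at 12 to 15 months against MENVEO at 12 months, PPAS3 accepts those windows, and SAP 5.2.3.5 uses 12 months in its title for a set sampled around 12 to 15 months. On that view 12 months is a nominal visit label. This explains the schedule, but it does not remove the timing difference from a table that compares the vaccines.

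A reader might infer that PPAS2 causes the imbalance. It does not. All the intervals above are in window, so adding the scheduled Visit 5 and 6 windows to PPAS2 would leave them unchanged. The missing limit matters only for off-schedule samples, and the PPAS2 item on other violations would not catch a 1a sample drawn on schedule at 15 months.

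A reader might also infer that MenACYW persistence will be understated. The documents give neither actual visit timing nor a waning rate. If nearly all 1a visits fall at 12 months, the effect is near zero.

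Nor is the overlap between 1a and 1b a defect. Objective 6 explicitly compares ages 12 to 15 months with 15 to 18 months, persistence included, so the spread belongs to the stated comparison.

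Finally, restricting the analysis to samples at 12 months keeps essentially all on-schedule 2a children but perhaps a quarter of 1a. That is selection after randomization in one arm, and it should not be the lead analysis. SAP 5.1.3 also leaves room for analyses beyond those listed, but room is not pre-specification.

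**Conclusion.** The point holds in conditional form. The Visit 5 schedule lets 1a be sampled up to about three months later after dose 3 than 2a, PPAS2 sets no limit on sample timing, and no planned analysis accounts for the interval. Whether this distorts the result depends on two unknowns, waning and actual visit timing. Under the assumed half-lives, the 1a/2a GMT ratio from timing alone is about 0.70–0.92 with uniform visits and 0.94–0.98 with visits clustered at 12 months. Objective 3 carries no hypothesis, margin or power calculation, so no alpha or sample-size figure changes. Any bias from waning would be against MenACYW and would not create a falsely favourable claim for it. This is a worthwhile descriptive improvement, not a threat to the primary conclusions.

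**What to change.** In the SAP:
- Keep full PPAS2 as the main persistence table.
- Tabulate months from dose 3 to the persistence sample by subgroup. This shows directly whether the concern is material.
- Add a supportive 1a vs 2a comparison of log10 hSBA titer adjusted for months since dose 3. It uses every child. Beyond about 7.6 months there are no on-schedule 2a data, so the adjustment there relies on the model.
- Add an age-matched sensitivity table restricted, in both subgroups, to samples drawn from 12 months to the day before 13 months. State its downside: a smaller 1a sample and possible selection by visit timing.
- Reconcile the 12-month wording of Objective 3 and Table 5.3 with the 1a Visit 5 window. This review takes no position on which should change.

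Scheduled Visit 5 and 6 windows may be added to PPAS2 to remove off-schedule samples, but they should not be presented as correcting the imbalance.

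The cost is SAP wording and a few descriptive tables from dates already collected. No visit, dose or sample changes.
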